While it is possible that there may be no direct benefits to participants, the potential benefits of the research to the participants are significant. Their craving or stress may improve significantly as a result of being part of the study. The process of participating in the MORE-VR could enhance self-efficacy. Participants may learn improved methods of managing OUD from each other's experience. Therefore, it is expected that participants may experience significant benefit from participating in the research study. The potential benefits to other individuals with OUD are also significant. The results of this research may provide credible evidence about the effects of MORE-VR for patients with OUD and whether it may be usefully integrated with conventional care in order to effectively manage opioid misuse and addiction.

3. Are there any costs to the participants from participation in research?

Yes No

If yes, specify:

4. Is there any compensation to the participants?

Yes No

a. If yes, answer the following:

Specify overall amount:

\$250

b. Specify when participants will be paid (e.g. at each visit, at end of study, etc.):

Participants will be paid at each visit.

c. If applicable, please specify payment by visit or other time interval (e.g. \$10 per visit, etc.):

Participants will be paid \$25 for the baseline and post-treatment assessment, \$20 per MORE-VR session, plus an additional \$40 bonus for completing 5 or more MORE-VR sessions.

d. If applicable, explain plan for prorating payments if participant does not complete the study:

Payment will be prorated according to how many study sessions are completed.

PI: [name] PhD/Associate Professor and Associate Director of Integrative Medicine

Title: Digital Therapeutic Development of Virtual Cognitive-Affective Training for Opioid Use Disorder

7. HIPAA and the Covered Entity

1. Does this study involve Protected Health Information (PHI) or de-identified health information?

Yes No

a. Select the method(s) of authorization that will be used:

Waiver or Alteration of Authorization

b. Will PHI be disclosed outside the Covered Entity?

Yes No

To whom?

FDA

And for what purposes?

Because this study involves the use of an investigational medical device, the FDA may receive PHI.

Does this study involve any of the following:

2. The investigational use of a drug?

Yes No

3. The investigational use of a medical device?

Yes No

4. Is this an investigator-initiated drug or device trial lead by the Principal Investigator?

Yes No

5. Exposure to radioisotopes or ionizing radiation?

Yes No

6. A Humanitarian Device Exemption (HDE)?

Yes No

7. Genetic testing and/or analysis of genetic data?

Yes No

8. Creating or sending data and/or samples to a repository to be saved for future research uses?

Yes No

9. Are you:

- Collecting samples of blood, organs or tissues from participants for research purposes;
- Introducing Recombinant or Synthetic Nucleic Acids (e.g. viral vectors, oligonucleotides) or cells containing recombinant nucleic acids (e.g. CAR-T) into participants; OR
- Introducing other biological materials (e.g. bacteria, viruses) into participants.

Yes No

10. Does this study involve any of the following?

- Cancer Patients
- Cancer Hypothesis
- Cancer risk reduction
- Cancer prevention

Yes No

11. Any component of the Clinical and Translational Science Institute (CTSI)?

Yes No

The Clinical Research Center (CRC)?

Yes No

IRB_00141495

Created: IRB_00141495
2/27/2021 - Request for Waiver of Authorization
11:56 AM

PI: [name] PhD/Associate Professor and Associate Director of Integrative Medicine

Submitted:
3/9/2021

Title: Digital Therapeutic Development of Virtual Cognitive-Affective Training for Opioid Use Disorder

Request for Waiver or Alteration of Authorization

Request for Waiver of Authorization for Recruitment Only

This option must only be used if you are reviewing PHI in order to identify eligible participants BEFORE approaching them to obtain consent and authorization. All other waiver requests must be entered below.

Waiver of Authorization for Recruitment Requested

Other Requests for Waivers of Authorization:

- Click "Add" below to add a new waiver request to this application.
- Click the waiver name link to edit a waiver that has already been created.
- To delete a waiver request, contact the IRB.

Date Created

Type of Request

Purpose of Waiver Request

There are no items to display

PI: [name] PhD/Associate
Professor and Associate
Director of Integrative
Medicine

Submitted:

3/9/2021

Title: Digital Therapeutic Development of
Virtual Cognitive-Affective Training for
Opioid
Use Disorder

Request for Waiver or Alteration of Authorization

Request for Waiver of Authorization for Recruitment Only

The PI must agree to the terms of this waiver request as described on this page. When the PI uses the "Submit" activity to submit the application for IRB review, a checkbox to accept the terms will be available in the "Submit" activity window.

This waiver request includes justification for waivers of consent for recruitment only, according to 45 CFR 46.116(d).

Terms for the Waiver of Authorization:

- › The purpose of this waiver of authorization is to allow for the use of PHI in order to identify and recruit individuals who may be eligible to participate in the specific research described in this IRB application. The waiver of authorization is necessary to accommodate this minimal-risk research activity prior to seeking a full authorization from research participants.
- › Methods for identifying individuals may include the following:
 - Reviewing medical charts
 - Reviewing databases that include PHI
 - Reviewing other medical- or health-based documents that include PHI
- › Identifiable information used under this waiver may include the following, as this is the minimum necessary for identifying eligible individuals:
 - Name
 - Contact information, such as phone number, address, or email address
 - An ID number, such as MRN or SSN
 - Date of birth
 - Medical and health information that may determine study eligibility
- › Any PHI recorded by the study team will only be used for recruitment and determining study eligibility. After this has been completed, the PHI must be removed from the research record or destroyed, unless the participants have given authorization for continued use of the PHI.
- › PHI will only be viewed by approved members of the study team and will not be disclosed for research purposes to any individual or institution without the participants' authorization for such use and disclosure of the PHI.
- › PHI will be stored in a secure manner according to HIPAA privacy and security provisions.

PI: [name] PhD/Associate Professor and Associate Director of Integrative Medicine

Submitted:
3/9/2021

Title: Digital Therapeutic Development of Virtual Cognitive-Affective Training for Opioid Use Disorder

8. Resources and Responsibilities

1. * State and justify the qualifications of the study staff:

Utah Principal investigator: [name], LCSW, is a licensed clinical social worker with 16 years of post-licensure experience and Associate Dean for Research and Professor, College of Social Work at the University of Utah, Director of the Center on Mindfulness and Integrative Health Intervention Development: oversee all research activities; hire, train, and supervise study staff; triage adverse events; manuscript preparation. [name] is the developer of MORE who has led 8 successful RCTs and multiple psychophysiological studies of MORE as a treatment for OUD, opioid misuse, and other addictive behaviors.

[name] (Utah Co-I) is Senior Strategic Statistician at University of Utah who has been PI on 5 NIH-funded studies and Director of Biostatistics Core on 2 NIH program projects. [name] will perform blinded statistical analyses of outcome data.

Study personnel: Study personnel include postdoctoral fellows, graduate research assistants, and undergraduate research assistants. All personnel are well-trained in study procedures and have experience in prior clinical trials of MORE and mindfulness for opioid misuse and addiction.

2. * Describe the training that study staff and investigators will receive in order to be informed about the protocol and understand their research-related duties and functions:

The entire study team has completed an IRB-approved human subjects training course and is knowledgeable about issues covered in the training. All investigators and research assistants will be trained by the PI on data collection and protocol in handling PHI. The PI has developed a training protocol for research assistants to learn all lab procedures. The training protocol involves:

1. Completing a mock assessment in the role of a "subject" as conducted by trained personnel;
2. Shadowing trained personnel for two assessments with actual participants;
3. Conducting an assessment while supervised by trained personnel until complete proficiency is attained; and
4. data review by the PI to ensure quality data collection with no mistakes

3. * Describe the facilities where the research activities will be performed (e.g. hospitals, clinics, laboratories, classrooms/schools, offices, tissue banks, etc.).

A private psychophysiology laboratory at the Center on Mindfulness and Integrative Health Intervention Development (C-MIIND), University of Utah.

A private treatment room at Highland Ridge Hospital.

No data will be shared with external collaborators until all needed agreements are in place with the UU's Partners for Innovation, Ventures, Outreach &Technology, or PIVOT Center.

4. * Describe the medical or psychological resources available at this site (and other participating sites, if applicable) that participants might require as a consequence of the research. If not applicable, please state.

Licensed clinical psychologists and licensed clinical social workers are on staff at both locations to provide psychological resources as needed. At Highland Ridge Hospital, physicians and nurses are available to provide medical resources as needed. At C-MIIND, medical resources can be provided by Madsen Health Center, which is a 3 minute drive away.

PI: [name] PhD/Associate Professor and Associate Director of Integrative Medicine

Submitted:
3/9/2021

Title: Digital Therapeutic Development of Virtual Cognitive-Affective Training for Opioid Use Disorder

Documents and Attachments

If any of your documents (such as investigational brochures, sponsor protocols, advertisements, etc.) are not available in an electronic format, please scan and save them as PDF files or contact our office for assistance.

Naming Documents: Please use the title field to clearly indicate the content of each form. The name you enter will be listed on your approval letter. Use names that will differentiate from earlier versions.

Examples:

Consent Document Control Group 04/14/05

Consent Document Treatment Group 4/14/05

Sponsor Protocol 04/14/05 Version 2

Assent Document(Highlighted Changes)

[Apple/Macintosh Users: MS Word documents must have a .doc file extension. See ERICA home page for instructions.](#)

[Print View: IRB Draft Protocol Summary](#)

eProtocol Summary:

Name	Version	Date Created	Date Modified	Date Approved
There are no items to display				

Consent Documents, Consent Cover Letters, Consent Information Sheets, Consent Scripts, etc.:

Name	Version	Date Created	Date Modified	Date Approved
There are no items to display				

Parental Permission Documents:

Name	Version	Date Created	Date Modified	Date Approved
There are no items to display				

Assent Documents:

Name	Version	Date Created	Date Modified	Date Approved
There are no items to display				

VA Consent Documents:

Name	Version	Date Created	Date Modified	Date Approved
There are no items to display				

Surveys, Questionnaires, Interview Scripts, etc.:

Name	Version	Date Created	Date Modified	Date Approved

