6. The VR system will capture trace data through logs that capture behavioral engagement with each intervention component. These will include the number of digital object manipulations, clicks, and eye tracking of fixation duration on digital objects

7. At the 8 weekly MORE-VR sessions, the following measures will be administered, for a total of 8 assessments:

a) **Craving** will be evaluated with a Numeric Rating Scale and the Desires for Drug Questionnaire,⁷² and **affect** will be evaluated with the

Positive and Negative Affect Scale (PANAS).⁷³

b) Coping self-efficacy will be measured with the Drug Taking Confidence Questionnaire,⁷⁴ which predicts heroin relapse.⁷⁵

c) Mindfulness will be evaluated with the Toronto Mindfulness Scale⁷⁶ as a therapeutic process measure and manipulation check.

d) Participants will complete a daily symptom diary of opioid craving, drug use and mood symptoms as well as mindfulness skills via ecological momentary assessments (EMA) delivered via the participant's own smartphone or home computer up to 3 times per day (morning, noon and evening).

e) Also at this post-treatment assessment, we will again administer the following questionnaires: the DASS, the TAPS, SHAPS, MPODS, NADA, the Ways of Savoring Checklist, and the Emotion Regulation Questionnaire.

f) Participants will participate in a semi-structured qualitative interview (sample questions attached as an additional document) about the acceptability of the MORE-VR system (e.g., "What did you like best? What didn't you like?" "What would you change?"). The interview will be audio-recorded and transcribed for analysis of intervention acceptability.

g) Safety will be assessed throughout to monitor adverse events.

7. Are all procedures for research purposes only (non-standard or non-standard of care procedures)?

Yes No

If no, list the procedures that are performed for research purposes only (non-standard or non-standard of care procedures):

8. Is there a safety monitoring plan for this study?

Yes No

9. Provide a summary of the statistical methods, data analysis, or data interpretation planned for this study. Factors for determining the proposed sample size (e.g., power) should be stated.

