All reported symptoms that subjects attribute to the study interventions will be documented and investigated by the PI (who has over a decade of clinical expertise with persons with substance use disorders and chronic pain, as well as clinical research experience through several NIH-funded clinical trials), and reported immediately to the University of Utah IRB. Risks associated with mindfulness meditation are minimal. There is no evidence that mindfulness worsens the symptoms causes complications with opioid therapy. The relaxation experienced as part of mindfulness training is sometimes associated with transient sleepiness, lasting no more than a few hours.

Participation in mindfulness meditation may also increase awareness of anxiety. Participants will be advised to inform the therapists of any significant shift in their symptoms for the worse while taking part in the interventions. Reports of such changes will be given to the PI, who will coordinate to interview the subject and make a determination of need concerning specific medical care or removal from the study. Events of this type are very uncommon, usually transient and pose minor barriers to the completion of this study.

Participants may interpret the interventions as substitutes for usual, conventional medical care. All participants will continue to receive the same medical care from their physician that they would otherwise receive. They will be informed that they should continue such care just as if they were not enrolled in a study. Participants will be asked to inform study personnel if there is a change in medications or other medical care during the trial (both during treatment and follow-up), but patients and their physicians will not be dissuaded from changing medical management practices.

While strict precautions will be implemented to protect patient confidentiality (detailed in the data monitoring plan in section 5 of the IRB application), there is the potential risk of a loss of confidentiality. Because potential participants will be asked about drug use, this could pose a risk to the participants given the illegal nature of their actions.

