The consent form will clearly specify that it is the option of the PI and the research team to withdraw a subject from the study should they prove to be a danger to self or others, or a significant disruption to the group. If participants appear intoxicated (as determined by meeting DSM-5 diagnostic criteria for alcohol, cocaine, opioid, amphetamine, or hallucinogen intoxication) or actively suicidal during study assessments or VR sessions, they will not be allowed to continue that session. Instead, they will be referred to the appropriate University of Utah Primary Care Clinic or Highland Ridge Hospital to receive medical evaluation by a physician, brief intervention by a psychologist or social worker, and more extensive mental health services, as needed. Alternatively, if the participant is determined to be a danger to self or others due to suicidal ideation or intoxication, university police will be alerted. Afterward, the PI will contact the participant in question and interview them to determine whether their substance use warrants exclusion from the study.

Another risk relates to the potential for cybersickness, which is a side effect associated with the use of VR technology. Cybersickness is associated with a range of symptoms including nausea, dizziness, disorientation, headaches, sweating, and/or eye strain.

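### Stopping MORE-VR for worsening or substance use can also end study participation, with no stated follow-up, so safety and acceptability data may be lost from those who did worst

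*Combined protocol and SAP*

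**What the plan says.** Section 6 (Risks and Benefits), item 1, contains four separate rules.

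- **Worsening symptoms.** The PI interviews the participant and is to "make a determination of need concerning specific medical care or removal from the study". The plan adds: "Events of this type are very uncommon, usually transient and pose minor barriers to the completion of this study".
- **Danger or disruption.** The PI and team may "withdraw a subject from the study should they prove to be a danger to self or others", or if they seriously disrupt the group.
- **Intoxication or active suicidality, immediate step.** Such participants are referred for care and "they will not be allowed to continue that session".
- **Intoxication or active suicidality, later step.** Afterwards "the PI will contact the participant in question and interview them to determine whether their substance use warrants exclusion from the study". No criterion is given for that decision.

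The measurement schedule is in Section 4 (Study Information), item 6, step 7. It opens: "At the 8 weekly MORE-VR sessions, the following measures will be administered, for a total of 8 assessments". Craving and affect are in that set (7a). Step 7d says: "Participants will complete a daily symptom diary of opioid craving, drug use and mood symptoms as well as mindfulness skills", on the participant's own device, up to three times a day. Step 7e begins: "Also at this post-treatment assessment, we will again administer the following questionnaires". Step 7f is the acceptability interview, and 7g says that safety is assessed throughout. Section 4, item 9, promises REML on all observed values in an intent-to-treat spirit. None of these places says what is collected once a person has been removed or excluded.

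**The concern.** Stopping an intervention and ending participation in a study are different decisions. The first is a clinical matter for the PI. The second also ends observation unless the plan says otherwise. Here the reasons for removal (substance use, worsening symptoms) overlap with what the pilot records: drug use and mood in the diary, distress and substance use in the post-treatment questionnaires, and adverse events. Any loss would therefore fall on people selected for doing badly.

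Aim 2 (Section 1, item 6) is to evaluate safety, usability and satisfaction, and there is no control arm. Each participant is 1/30 = 3.3% of the safety denominator and of the interviews. A person stopped for worsening may also be among the most informative about whether a prototype is tolerable. REML uses every value it is given, but it cannot supply an adverse event or an interview that was never collected.

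**Working it through.** **Figures in the plan.** The plan gives no removal rate or dropout allowance to reproduce. The one related figure, total compensation in Section 6, item 4, does reproduce: 25 + 25 + 8 × 20 + 40 = $250. The $25 for the post-treatment assessment is therefore already in the total.

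**Data at risk.** Taken from the plan: N = 30, 8 weekly sessions, up to 3 diary prompts a day. Assumed: 1 or 2 people removed, the first lost session equally likely to be any of sessions 2 to 8, and a diary that runs all 8 weeks.

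- Sessions lost per person: (7 + 6 + 5 + 4 + 3 + 2 + 1)/7 = 4.
- Session ratings: 4 or 8 of 30 × 8 = 240, which is 1.7% or 3.3%.
- Diary prompts: 3 × 7 × 4 = 84 per person, so up to 84 or 168 of 3 × 7 × 8 × 30 = 5,040.
- Interviews and post-treatment questionnaire sets: 1 or 2 of 30.

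**Would the craving trend be distorted?** Inputs: r = .30 from Section 4, item 9, unit total variance, a random-intercept model, and time scaled from 0 (session 1) to 1 (session 8).

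- Sum of squared time deviations per person: 42/49 = 0.857.
- Slope standard error on full data: √[0.70/(30 × 0.857)] = 0.165 SD. After the cut it is 0.167 (1 removed) or 0.169 (2 removed).

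The shift is the full-data slope minus the slope on data cut at removal, averaged over all removal times. Plus means that the cut data look too favourable. For one person with a sustained 1 SD rise starting at the first lost session, the deviations summed from that session onward are 0.500, 0.857, 1.071, 1.143, 1.071, 0.857 and 0.500 for sessions 2 to 8. Their mean is 0.857, so the shift is 0.857/(30 × 0.857) = 0.0333. The other rows use the same method.

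| Assumed course of craving | 1 removed, per 1 SD | 2 removed, per 1 SD | 2 removed, rise of 0.5 to 1.5 SD |
|---|---|---|---|
| Sustained rise, all after removal | +0.0333 | +0.0667 | +0.03 to +0.10 |
| Sustained rise, first bad week recorded | +0.0275 | +0.0546 | +0.03 to +0.08 |
| Two-week rise, all after removal | +0.0075 | +0.0151 | +0.008 to +0.023 |
| Two-week rise, first week recorded | −0.0031 | −0.0065 | −0.003 to −0.010 |

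The largest shift is 0.10/0.165 = 0.61 of a standard error. The two-week cases, closest to the plan's own description of such events, reach at most 0.023/0.165 = 0.14, and the sign depends on whether the first bad week was recorded.

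**The case against.** The strongest reply is that this point rests on silence in a text that is only partly available. Section 6, item 1, says that the consent form will set out the withdrawal option, and that form was not available. Section 4, item 8, asks whether a safety monitoring plan exists, and the answer cannot be read. Follow-up after removal could be described in either place. Section 6, item 1, also has the PI document and investigate every symptom that participants attribute to the intervention, and it mentions a follow-up period. With step 7g, that gives partial support for continued safety reporting. All of this stands. A reader might infer that the plan forbids or abandons safety follow-up of removed people; the documents do not say so. They only fail to provide for it expressly.

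A second reply is that the exclusion interview may apply only to dangerous cases, because the sentence just before it concerns them. The wording is ambiguous. On that reading fewer people are affected, and more of them would meet an unsafe-contact exception.

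A third reply is that the numbers are small and assumed, which is correct. A reader might infer that exclusion makes craving look better than it is. The calculation does not support that: the sign changes with the assumed course, and the plan itself says that the pilot is not powered for proximal outcomes. Nor is the planned analysis faulty on this account, since values recorded before removal stay in the model.

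Finally, it may seem natural to collect craving and affect remotely after sessions stop and add them to the mixed model. That would mix assessment setting with time and change what is estimated, because item 9 targets change across the eight sessions. This is debatable and is not recommended here.

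**Conclusion.** The point holds as a low-severity improvement. The two rules end study participation for reasons tied to what the pilot measures, and the available text does not continue observation afterwards. The likely loss is 1 or 2 of 30 interviews and questionnaire sets, up to 84 or 168 diary prompts, and an unknown number of later adverse events. These counts rest on an assumed number and timing of removals. The triggering event is not itself lost, and most foreseen VR risks, such as sleepiness, cybersickness and cue distress, would appear at the session. The conclusion rests on completeness of safety and acceptability data, not on the craving slope. If the consent form already provides for follow-up, what remains is to align Section 6 with it. The pilot stands without the change.

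**What to change.** In Section 6, item 1, reword the outcome of the worsening-symptoms rule and of the substance-use interview as discontinuation of MORE-VR sessions, and leave that clinical decision with the PI. Then add the following:

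- Unless consent is withdrawn, or contact is unsafe or clinically inadvisable, adverse-event monitoring and the planned diary continue through week 8.
- The post-treatment questionnaires and exit interview are offered, remotely if needed, with the $25 post-treatment payment.
- Everyone who starts a session stays in the safety analysis, and each discontinuation is reported with its reason.
- Off-treatment craving or affect ratings are not required in the primary mixed model. If any are collected, they are reported descriptively or as a sensitivity analysis.

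The cost is a few lines in the protocol and consent form, and one line on payment because Section 6, item 4, prorates by sessions completed. There would be a few extra contacts. The procedures are already planned and the $25 is already inside the $250. The downsides are some burden on the few people affected, some refusals, and results that may look slightly less favourable.

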instructions on the OSP website.***Link to a Proposal ID/DSS through eAward****Proposal ID/DSS:** 10058817**PI:** [name]**Sponsor:** BEHAVR**Prime Sponsor:** NIH NATIONAL INSTITUTE ON DRUG ABUSE**Department:****Short Title:** BEHAVR R43/R44 SUBAWARD**Sponsor Award Number:** 10058817**Type:** Industry**Award Start Date:** 5/15/2021**Award End Date:** 4/30/2022**Prime Sponsor Type:** Federal Government

PI: [name] PhD/Associate Professor and Associate Director of Integrative Medicine

Submitted: 3/9/2021

Title: Digital Therapeutic Development of Virtual Cognitive-Affective Training for Opioid Use Disorder

3. Participants

1. **Ages of Participants:**

18 and older (Consent form needed)

2. **Specific age range of participants (e.g., 7-12 years old, 60+, etc.):**

18+

3. **Indicate any vulnerable participant groups (other than children) included:**

None

If "Other", please specify:

If "None" and no children are involved, answer the following question.

Has the participant selection process overprotected potential subjects who are considered vulnerable so that they are denied opportunities to participate in research?

Yes No

4. **Number of participants to be included and/or enrolled in this entire study, across all study locations:** 30 enrolled; 1000 screened

5. **Characteristics of Participants/Inclusion Criteria:**

Inclusion criteria: 1) Men/women 18+ years of age, 2) current DSM-5 Opioid Use Disorder diagnosis as assessed with the Mini-International Neuropsychiatric Interview (MINI), and 3) in treatment for opioid use disorder.

6. **Participant Exclusion Criteria:**

1) Mindfulness intervention experience, 2) active psychosis or suicidality on the MINI); 3) reports, or is noted by clinical or study staff as showing cognitive impairment; 4) unwilling or unable to remain in OUD treatment for the duration of the trial (e.g., planned relocation, pending incarceration, etc.).

7. **Is a substantial percentage of the participant population anticipated to be non-English speaking?**

Yes No

PI: [name] PhD/Associate Professor and Associate Director of Integrative Medicine

Submitted:

3/9/2021

Title: Digital Therapeutic Development of Virtual Cognitive-Affective Training for Opioid Use Disorder

4. Study Information

1. Design of Study (select all that apply):

Non-Experimental and/or Descriptive Research Design:

There are no items to display

Experimental and/or Interventional Research Design:

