The final risk relates to the measurement protocol. Because the virtual drug cue exposure and negative emotion regulation protocols involve the presentation of opioid-related cues and stressful experiences, there is a risk that they could trigger opioid cravings and psychological distress. Yet, it is very unlikely that such craving or distress will exceed that which would occur on an everyday basis, given that opioid cues (e.g., the sight of a heroin needle) are present in participants' natural environments. To monitor for potential risk, participants will be asked to rate their stress and craving on two 10-point visual analogue scales (1 = none, 10 = extreme) before and after the virtual cue exposure and negative emotional regulation protocols, and then again at the end of the assessment session. In the unlikely event that participants report stress or craving resulting from cue exposure as determined by an elevation in craving or stress by 3 points from baseline levels that maintains at the end of the assessment, the PI will notify the University of Utah IRB, and make a referral for clinical services, as appropriate. To mitigate this risk, the Study Coordinator/Research Assistant (a master's level social worker) will be trained by the PI (a licensed clinical social worker and clinician with over 16 years of experience) to debrief participants, assess risk, and provide 15 minutes of progressive muscle relaxation to ensure subjects have experienced a reduction in stress or craving to a level of within 3 points of their baseline level on the visual analogue scales upon beginning the psychophysiological protocol. In two four RCTs of MORE with persons with substance use disorders, the PI used a similar risk management strategy for a psychophysiological cue-reactivity protocol, and no participants remained distressed after this procedure.

2. Describe the potential benefits to society AND to participants (do not include compensation):

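### The only score-based trigger for cue-exposure distress needs a 3-point rise on a scale that stops at 10, so it cannot be met on a scale where the participant starts above 7

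*Combined protocol and SAP*

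**What the plan says.** All of the rule is in Section 6, Risks and Benefits, item 1. Stress and craving are rated on "two 10-point visual analogue scales (1 = none, 10 = extreme) before and after the virtual cue exposure" and negative-emotion protocols, and once more when the session ends. The trigger is "an elevation in craving or stress by 3 points from baseline levels that maintains at the end of the assessment". When it is met, the investigator notifies the IRB and refers for clinical services as appropriate.

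As mitigation, trained staff are "to debrief participants, assess risk, and provide 15 minutes of progressive muscle relaxation", with the aim of bringing stress or craving down to "a level of within 3 points of their baseline level on the visual analogue scales". Baseline is tied there to the start of the psychophysiological protocol, so I read it as the pre-exposure rating.

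Other protection that does not depend on the ratings:

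- Section 6, item 1: "All reported symptoms that subjects attribute to the study interventions will be documented and investigated" by the investigator. The same sentence goes on to require that they be reported to the IRB without delay. Participants are also told to report any marked worsening.
- Section 6, item 1: a participant who appears intoxicated is stopped and referred. So is one who is "actively suicidal during study assessments or VR sessions, they will not be allowed to continue that session".
- Section 4, Study Information, item 6: "Safety will be assessed throughout to monitor adverse events".
- Section 8, Resources and Responsibilities, item 4: licensed psychologists and social workers are on staff at both locations.

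The exclusions in Section 3, item 6 begin "1) Mindfulness intervention experience, 2) active psychosis or suicidality on the MINI". Neither they nor Section 6 caps the rating with which a participant may enter the exposure.

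**The concern.** The trigger is purely a change from baseline on a bounded scale. No absolute level prompts action, and there is no separate rule for a high start. The higher a participant starts, the less room there is to register a rise, and above 7 there is not enough room to reach 3 points.

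A participant with opioid use disorder who goes from 8 to 10 during drug-cue exposure, and is still at 10 at the end, has worsened to the point labelled extreme. On that scale the rule stays silent. The relaxation goal has the same form, so it does not ask for any reduction either. Safety is one of the three stated foci of this pilot (Section 4, item 9), and this is the one place where the plan puts a number on exposure-related distress.

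**Working it through.** **Inputs**, all from Section 6, item 1: scale minimum 1, maximum 10; trigger a rise of 3 points, on craving or stress, still present at the end; relaxation goal within 3 points of baseline. The plan gives no figure of its own to reproduce here.

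**Step 1. Is the trigger reachable?** Maximum rise = 10 − start. The trigger needs 10 − start ≥ 3, that is, start ≤ 7.

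| Start | Maximum rise | 3-point trigger reachable? | Final 10 within 3 points of start? |
|---|---|---|---|
| 6 | 4 | yes | no |
| 7 | 3 | yes, only by reaching 10 | yes, at exactly 3 |
| 8 | 2 | no | yes |
| 9 | 1 | no | yes |
| 10 | 0 | no | yes |

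The limit is the same if ratings need not be whole numbers: a start of 7.1 leaves 2.9 points, and 7.5 leaves 2.5. If the rule meant strictly more than 3 points, a start of 7 would be out of reach as well.

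**Step 2. Which rises are lost to the ceiling?** In whole numbers, the rises from a start above 7 are 8 to 9, 8 to 10 and 9 to 10: three, and none can trigger. From a start of 10 no rise is possible. A move from 7 to 9 also fails to trigger, but not because of the ceiling: that participant could have reached 10 and met the rule.

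**Step 3. Does the relaxation goal catch them?** The goal is met when end − start ≤ 3. The largest value of end − start is 10 − start, which is 3 or less for every start of 7 or more. A final rating of 10 therefore satisfies the goal from any such start. At exactly 3 points, as in 7 to 10, a participant meets the goal and the trigger at once.

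**Step 4. Both scales.** The rule reads craving or stress. A participant is wholly outside it only if both ratings start above 7. With one high start, worsening confined to that scale goes unflagged, while the other scale can still trigger.

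**The case against.** **A change score suits the purpose.** The rule is meant to pick up distress caused by the exposure, and a high pre-exposure rating was not caused by it. Every change score on a bounded scale has a ceiling. This stands as a reason to keep the 3-point rule and to respond only to rises. It does not explain why a rise from 8 to 10 should go unnoticed.

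**Other routes exist, and one also ends at the IRB.** Symptom reporting in Section 6 carries no score threshold, so it may be broader than the trigger. Debriefing and risk assessment are not written as depending on a 3-point rise, and every participant must already be in treatment for opioid use disorder. This narrows the gap. But symptom reporting depends on the participant attributing the symptom to the study interventions, whereas Section 6 presents cue exposure as part of the measurement protocol. The other routes rest on self-report or staff judgement.

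**Earlier trials left nobody distressed.** Section 6 says so, under a similar strategy. It does not say how distress was defined. If a similar 3-point criterion was used, it could not have registered this case.

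**The rule may seldom operate.** The chronological procedures in Section 4, item 6 list no cue-exposure protocol. How often the rule would be applied is therefore unclear, but Section 6 describes the exposure as part of this study, and the rule should work while that text stands.

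A reader might infer that high starters are unprotected, or that they miss a referral that others receive automatically. The documents support neither. The routes above apply to them, and referral is made only as appropriate even when the trigger is met. The one unconditional consequence of the trigger is IRB notification.

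**Conclusion.** The point holds as a boundary failure in a stated safety rule. On any scale with a start above 7 the 3-point trigger cannot be met, and the relaxation goal is met even at 10. No other part of the plan supplies a score-based prompt for a participant who starts there and worsens.

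Its size is exact in scale values, three whole-number rises, and unknown in people. The documents give no distribution of pre-exposure ratings, so nothing supports a claim that many participants are affected, or that any will be. The result assumes that baseline means the pre-exposure rating and that a rise of exactly 3 points counts. It concerns monitoring of individual participants and does not touch the outcome analysis. I would label it a cheap improvement.

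**What to change.** Keep the 3-point rule as it is for IRB notification and add one sentence:

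> If the pre-exposure rating on a scale is above 7, any rise on that scale still present at the end of the session prompts clinician review before the participant leaves, with referral as appropriate.

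Restate the relaxation goal as less than 3 points above baseline and, for starts above 7, no higher than baseline. That removes the overlap at exactly 3 points and makes the goal mean something at the top of the scale.

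The before, after and end-of-session ratings are already planned, so no new data are needed. The cost is a few extra clinician reviews by staff already on site, some of them for one-point changes such as 9 to 10 that may be ordinary variation. For that reason the added sentence stops at clinician review and does not make such a change an IRB notification.
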